36	5.8.1 – Permitted therapy	Lixivaptan has the potential to inhibit the metabolism of CYP3A4 and CYP2C8 substrates, including atorvastatin and simvastatin, therefore care should be exercised when administering lixivaptan in combination with these substrates. In order to minimize the potential for AEs	Lixivaptan has the potential to inhibit the metabolism of CYP3A4 and CYP2C8 substrates, including atorvastatin, and simvastatin, and amlodipine . Therefore, care should be exercised when administering lixivaptan in combination with these substrates. In	Because inhibition of CYP3A4 by lixivaptan may reduce metabolism of amlodipine, a dosing limit has been added.

Page	Section	Version 4 dated January 9, 2019	Version 5	Comments
		
due to drug-drug interactions, prior to enrollment in the study, the Investigator, in consultation with the Medical Monitor, should consider potential dose adjustments or alternative therapeutic options that are not CYP3A4 or CYP2C8 substrates (e.g. rosuvastatin to replace simvastatin or atorvastatin) or that have a high therapeutic index. If subjects are receiving simvastatin as background medication and it is not possible to replace simvastatin with rosuvastatin, the dose of simvastatin should be decreased to < 20 mg daily in subjects who are administered the 50 mg BID dose of lixivaptan and < 10 mg daily in subjects who are administered the 200 mg BID dose of lixivaptan.
	
order to minimize the potential for AEs due to drug-drug interactions, prior to enrollment in the study, the Investigator, in consultation with the Medical Monitor, should consider potential dose adjustments or alternative therapeutic options that are not CYP3A4 or CYP2C8 substrates (e.g. rosuvastatin to replace simvastatin or atorvastatin) or that have a high therapeutic index. If subjects are receiving simvastatin as background medication and it is not possible to replace simvastatin with rosuvastatin, the dose of simvastatin should be decreased to < 20 mg daily in subjects who are administered the 50 mg BID dose of lixivaptan and < 10 mg daily in subjects who are administered the 200 mg BID dose of lixivaptan. If amlodipine is needed for clinical care, the dose should not exceed 5 mg daily.
	
37	5.8.2 Prohibited Therapy	
 Treatment with weak CYP3A4 or CYP2C8 inhibitors, including amlodipine, chlorzoxazone, cilostazol, fosaprepitant, istradefylline, ivacaftor, lomitapide, ranitidine, ranolazine, tacrolimus, ticagrelor, trimethoprim. For weak CYP3A4 or CYP2C8 inhibitors, medications may be allowed in consultation with the Medical Monitor; 	
 Treatment with weak CYP3A4 or CYP2C8 inhibitors, including amlodipine, chlorzoxazone, cilostazol, fosaprepitant, istradefylline, ivacaftor, lomitapide, ranitidine, ranolazine, tacrolimus, ticagrelor, trimethoprim. For weak CYP3A4 or CYP2C8 inhibitors, medications may be allowed in consultation with the Medical Monitor; 	
Amlodipine is a CYP3A4 substrate and not an inhibitor. Thus, it has been deleted from this section.

Page	Section	Version 4 dated January 9, 2019	Version 5	Comments
63	Table 21-1 Schedule of Assessments	Screening -30 to -3 or -2	Screening -44 to -3 or -2	Increased duration of Screening from 4 weeks to 6 weeks
64	Footnote 5 to Table 12-1 - Schedule of Assessments	5. Clinical labs: hematology, clinical chemistry (including liver function), and urinalysis at approximately the same time of day (in the morning and, on dosing days, before the lixivaptan dose). The list of analytes is shown in Table 6-1. .	5. Clinical labs: hematology, clinical chemistry (including liver function), and urinalysis at approximately the same time of day (in the morning and, on dosing days, before the lixivaptan dose). The list of analytes is shown in Table 6-1. Lab tests that need to be repeated during Screening may be obtained through the services of an at-home nursing service provided by the Sponsor.	Provides for the use of a home nursing service to draw blood if repeat lab tests are needed during Screening.
65	Footnote 18 to Table 12-1 - Schedule of Assessments	If a patient does not return to the site for PK sample collection after discharge on Day 8, this will not be considered a protocol deviation.	If a patient does not return to the site for PK sample collection after discharge on Day 8, but has the blood drawn by an at-home nursing service , this will not be considered a protocol deviation.	Indicates that if a subject does not come back for visits after Day 8, then it is not a protocol deviation only if the blood is drawn by the at-home nursing service.

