2.2 Study Endpoints

2.2.1 Primary Endpoints

- The following PK parameters will be calculated using noncompartmental methods, whenever possible, based on the plasma concentrations of lixivaptan and its major metabolites (WAY-141624, WAY-138451, and WAY-138758), for lixivaptan and each metabolite: maximum observed plasma drug concentration (C_{max}), time to reach maximum plasma concentration (t_{max}), area under the plasma concentration-time curve (AUC) from time 0 until the last quantifiable concentration (AUC_{0-t}), AUC extrapolated to infinity (AUC_{0-inf}), terminal elimination phase half-life ($t_{1/2}$), apparent terminal elimination rate constant (λ_z), total body clearance (CL/F; lixivaptan only), and volume of distribution (V_z/F ; lixivaptan only).
- The safety and tolerability of lixivaptan will be assessed through evaluation of physical examination findings, vital signs, 12-lead electrocardiograms (ECG), clinical laboratory findings (clinical chemistry, hematology and urinalysis), assessments of adverse events (AE) and a questionnaire assessing aquaretic tolerability (symptom burden of nocturia, urgency, frequency).

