4.2.1 Reasons for Withdrawal/Discontinuation

Subjects may withdraw from the study at any time and for any reason without prejudice to their future medical care by the Investigator or at the study site. Every effort should be made to keep subjects in the study and, in the case of voluntary withdrawal, to inquire as to the reason(s) for withdrawal. The reasons for subjects not completing the study will be recorded.

If a subject withdraws for any reason after having received study drug, the subject will be asked to complete ET procedures, which will be the same as those scheduled to be performed prior to discharge from the CRU on Day 8. If a subject voluntarily withdraws before receiving the study drug, no additional safety assessments or testing will be required.

A subject may be withdrawn from the study for any of the following reasons:

1. Does not meet the protocol inclusion or exclusion criteria.
2. Noncompliance with the protocol.

3. A serious or intolerable AE that, in the Investigator's opinion, requires withdrawal from the study, including but not limited to laboratory safety assessments that reveal clinically significant (CS) hematological or biochemical changes from the baseline values, other than changes that are expected for vasopressin antagonists, and symptoms or an intercurrent illness that justifies withdrawal. Mild elevations in serum creatinine or serum sodium are known pharmacodynamic effects of vasopressin antagonists like lixivaptan and are transient and reversible. Therefore, patients should not be withdrawn due to mildly elevated serum creatinine or serum sodium. Cases where eGFR has declined by 25% or more from baseline should be discussed with the Medical Monitor.
4. Lost to follow-up.
5. Other (e.g., pregnancy, development of contraindications of use of study drug).
6. The subject withdraws consent, or the Investigator or Sponsor decide to discontinue the subject's participation in the study.
7. The Investigator will also withdraw a subject if the Sponsor terminates the study.

Upon occurrence of a serious or intolerable AE, the Investigator will confer with the Sponsor. If a subject is discontinued because of an AE, the event will be followed until it is resolved or stable as determined by the Investigator. Any subject may withdraw his or her consent at any time.

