4.2.3 Replacements

If the Investigator withdraws a subject for a reason related to the study drug (in the opinion of the Investigator), then the subject is considered discontinued from the study. Discontinued subjects will be replaced if deemed necessary by the Sponsor.

If a subject does not complete the study for a reason that is unrelated to the study drug, the subject may be replaced if the Sponsor instructs the site to do so. The decision regarding the replacement of subjects will be documented.

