6.1.8 Questionnaire for Tolerability

A questionnaire will be provided in the study reference manual that will assess how well patients tolerate aquaresis-associated events due to the planned lixivaptan doses. The questionnaire will be completed at 2 timepoints as specified in the study schedule of assessments ([Table 12-1](#)).

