12.2 Appendix 2: Schedule of Assessments

Table 12-1 Schedule of Assessments

Visit type:		Screening ¹⁷	Admit ¹⁷	In-CRU	In-CRU	Discharge after AM Assessments		PK Visit in AM		PK Visit in AM; Admit for PM dose	In-CRU	Discharge after PK Collection and Assessments	PK Collection ¹⁸	End of Study Visit
Procedure:	Study Day:	-44 to -3 or -2	-2 or -1	-1	1	2	3	4	5	6	7	8	9-11	35 ±2
Informed Consent		X												
Demographics		X												
Medical History		X												
Serum/Urine Pregnancy Test ^{1,2}		X	X											X
FSH ³		X												
Height/Weight/BMI		X												X
Inclusion/Exclusion		X												
Previous Medications ¹		X	X											
Concomitant Medications ⁴		X		X	X	X		X		X	X	X	X	X
Clinical Lab Evaluations ⁵		X		X	X	X					X	X		X
Serum Creatinine ⁶		X		X	X	X					X	X		X
Electrocardiogram ⁷		X			X							X		
Vital Signs ⁸		X		X	X	X		X		X	X	X		X
Physical Examinations ^{1,9}		X	X									X		X
Adverse Events ¹⁰								X						
Daily Fluid Intake ¹¹				X	X	X (AM only)					X	X (AM only)		
Administer Dose in-CRU ¹²					AM PM	AM		AM		AM PM	AM PM			
Self-Administer Dose ¹²						PM	AM PM	PM	AM PM					
PK Blood Samples ¹³					X	X		X		X	X	X	X	
Urine Osmolality ¹⁴				X	X	X					X	X		
Daily Urine Output ¹⁵				X	X	X (AM only)					X	X (AM only)		
Tolerability Questionnaire						X					X			
Plasma Copeptin ¹⁶				X		X					X			X
TKV and LV (by MRI)				X							X			X

Abbreviations: BMI= body mass index, CRU = clinical research unit, EOS = end of study, FSH = follicle-stimulating hormone, MRI = magnetic resonance imaging, PK = pharmacokinetic, Preg. = pregnancy, TKV = total kidney volume, LV = liver volume.

- ¹ Assessments will be performed on Day -1 or Day -2 for subjects admitted to CRU on Day -2.
- ² Serum pregnancy test to be performed at Screening; Urine pregnancy test to be performed at Day -2 or Day -1 and at End of Study.
- ³ Postmenopausal subjects with a urine pregnancy result outside the post-menopausal range or an indeterminate pregnancy test will undergo additional testing with FSH if necessary based on Investigator discretion to confirm postmenopausal status prior to study enrollment.
- ⁴ Includes over the counter medications.

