12.3 Appendix 3: Assessment Windows

Table 12-2 Assessment Windows

Procedure	Dosing Day	Window (units)
Lixivaptan PM dose	Day 1 – Day 7	In CRU: 10 hr ± 15 minutes after AM dose Self-Administered: 10 hr ± 1 hr after AM dose
	Assessment Day	
PK Blood Samples	Day 1, Day 2, Day 4, Day 6, Day 7, Day 8, Day 9, Day 11	- 60 minutes (predose Day 1) - 10 minutes (predose Day 7) ± 3 min (≤4 hr) ± 5 min (> 4 hr but ≤ 12 hr) ± 10 min (> 12 hr but ≤ 24 hr) ± 1 hr (> 24 hr but ≤ 48 hr) ± 2 hr (> 48)
Urine Osmolality and Urine Specific Gravity	Day 1-2, Day 7-8	Subjects will empty their bladders completely 15 ± 5 minutes prior to each scheduled collection, after which they will have 30 minutes to provide a spot urine sample. Subjects who will not be able to provide a sample within 30 minutes will be given an additional 30 minutes to do so and the different sampling time will be recorded.
Electrocardiogram	Screening, Day 1, Day 8	- 60 minutes (predose), ± 30 minutes (postdose)
Vital Signs	Screening, Day -1, Day 1, Day 2, Day 4, Day 6, Day 7, Day 8, Day 35	- 60 minutes (predose), ± 30 minutes (postdose)
Clinical Laboratory Samples	Screening, Day -1, Day 2, Day 7, Day 35	- 60 minutes (predose Day 2 and Day 7) In the morning on Day -1 and Day 35
Tolerability Questionnaire	Day 2, Day 7	Subjects will complete the questionnaire in the morning of Day 2, before discharge from the CRU, and in the morning of Day 7.
TKV and LV (MRI)	Baseline End of dosing End of study	Baseline: between Screening and Day -1 End of dosing: Day 7 or 8 or 9 End of study: Day 35 ± 2

Table abbreviations: hr = hours, PK= pharmacokinetic

Summary of Changes in the Conduct of the Study (from Section 9.8.1 of the Clinical Study Report, dated September 22, 2020)

Changes in the Conduct of the Study

There were 2 protocol versions that were not implemented or submitted to the IRB. Protocol versions 1 and 2 were marked final and dated 19 March 2018 but the version number 1.0 remained unchanged in the footer of both versions. Refer to Note to File (dated 23 February 2020) in Appendix 16.1.1 to distinguish between the 2 documents.

Protocol version 3 (dated 24 April 2018) was the first protocol version submitted to the IRBs and amended. There were 2 subsequent protocol amendments, versions 4 and 5, that were implemented after the first subject was enrolled. Copies of the protocol and protocol amendments are provided in Appendix 16.1.1. Brief summaries of the changes are outlined below.

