#### 16.7. OTHER SAFETY ASSESSMENTS

Tolerability data obtained from the Questionnaire for Tolerability will be listed for all subjects. Frequencies and proportions of responses to questions will be summarized by cohort and

Document: \\leedc-vnasc01\BIOSdata\Palladio\Lixivaptan\\WYA34000\Biostatistics\Documentation\SAP\PA-

102 SAP V1.0 NonPKPD 25APR2019
Author: [name]

Version Number: 1.0

Version Date: 25 April 2019

Template No: CS\_TP\_BS016 – Revision 5 Reference: CS\_WI\_BS005

Effective Date: 01Apr2018

Palladio Biosciences STATISTICAL ANALYSIS PLAN: PROTOCOL PA-102 Page 30 of 36

dose.

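### Neither early-termination assessment list includes the aquaretic tolerability questionnaire, so the Day 7 result understates burden where aquaresis is the reason for stopping

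*Protocol*

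**What the plan says.** - **Status of the instrument.** Protocol 2.2.1 lists, among the primary safety and tolerability measures, "a questionnaire assessing aquaretic tolerability (symptom burden of nocturia, urgency, frequency".
- **Timing.** Protocol 6.1.8: "The questionnaire will be completed at 2 timepoints as specified in the study schedule of assessments". Table 12-2 gives them: "Subjects will complete the questionnaire in the morning of Day 2, before discharge from the CRU, and in the morning of Day 7". In Table 12-1 the row "Tolerability Questionnaire" is marked under Day 2 and Day 7 only, and the table has no ET column.
- **ET visit.** Under protocol 4.2.1 a subject who withdraws after receiving drug is asked to "complete ET procedures, which will be the same as those scheduled to be performed prior to discharge from the CRU on Day 8". Under 4.2.2 those who discontinue treatment or withdraw have, where possible, the full set of end-of-study assessments instead.
- **Replacement.** Protocol 4.2.3, on withdrawals related to study drug: "Discontinued subjects will be replaced if deemed necessary by the Sponsor". Section 3.1 also allows replacement so that about 32 subjects complete, and 5.1 puts the replacement in the same cohort.
- **Analysis.** Non-PK/PD SAP 16.7: "Frequencies and proportions of responses to questions will be summarized by cohort and" dose. SAP 7.3 leaves missing data missing. SAP 6.1 lets percentages rest on the analysis set, on subjects with data, or on both. SAP 7.2 names aquaretic tolerability as a variable of the primary estimand and applies that estimand whether or not treatment is stopped early.

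**The concern.** The Day 2 form follows the two doses of Day 1. The Day 7 form follows the 12 doses of Days 1 to 6 (6 days × 2), so it is the only form that describes tolerability under sustained dosing. A subject who stops in between because nocturia, urgency or frequency became intolerable is the subject whose later answer matters most, and no scheduled visit collects it. For such stops the missingness depends on the outcome being measured.

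The study is meant to guide dosing recommendations (protocol 1.7), and Table 5-1 marks 200 mg BID as a candidate upper limit for tolerability. With 8 subjects per cohort, one or two lost answers change the Day 7 proportions noticeably. The estimand in SAP 7.2 asks for tolerability despite discontinuation, and for the questionnaire the schedule collects nothing at discontinuation to support it.

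**Working it through.** **1. The plan's own tolerability figure.** Table 7-1 gives the probability of missing an adverse event in 8 subjects. With (1 − p)^8 for p = 0.1, 0.2, 0.3, 0.4 and 0.5, the results are 0.4305, 0.1678, 0.0576, 0.0168 and 0.0039. The stated values (0.43, 0.168, 0.058, 0.017, 0.004) reproduce and are not in dispute. The calculation treats all 8 subjects as observed.

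**2. The schedule against the two ET definitions.**
- Days with a questionnaire (Tables 12-1 and 12-2): Day 2 and Day 7.
- ET as in 4.2.1: Day 8 discharge procedures. No questionnaire on Day 8.
- ET as in 4.2.2: end-of-study assessments. No questionnaire on Day 35.

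Under either definition, a subject who stops after the Day 2 form and before the Day 7 form gives no further answer.

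**3. Illustration of size.** The documents give no dropout rate, so these inputs are assumptions: 8 subjects answer on Day 7, 2 of them report high burden, and k others stopped earlier because of aquaresis, were replaced, and would have reported high burden.
- Subjects with data (allowed by SAP 6.1): 2/8.
- Safety Analysis Set (allowed by SAP 6.1; keeps replaced subjects): 2/(8 + k).
- Stoppers counted: (2 + k)/(8 + k).

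| k | Subjects with data | Safety Analysis Set | Stoppers counted |
|---|---|---|---|
| 1 | 2/8 = 25% | 2/9 = 22% | 3/9 = 33% |
| 2 | 2/8 = 25% | 2/10 = 20% | 4/10 = 40% |
| 3 | 2/8 = 25% | 2/11 = 18% | 5/11 = 45% |

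The larger denominator does not help. It keeps the stoppers in the count of subjects without recording their burden, so the shortfall is k/(8 + k) = 11%, 20% or 27%.

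**4. The same effect without replacement.** If 8 are dosed, 2 stop for aquaresis and 2 of the remaining 6 report high burden, the plan gives 2/6 = 33% or 2/8 = 25%, against 4/8 = 50%. Replacement does not create the gap. It brings the number of Day 7 responders back to 8, so the loss is harder to see in that table.

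**5. In rates.** Let q be the true share with intolerable aquaresis and w the share of those who stop before Day 7, with no other stops. The expected Day 7 share among subjects with data is q(1 − w)/(1 − qw). For q = 0.25 this is 0.20, 0.143 and 0 at w = 0.25, 0.5 and 1. Over the same range of w it runs from 0.077 to 0 for q = 0.1 and from 0.429 to 0 for q = 0.5.

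**6. Stops for other reasons.** If 2 subjects with low burden leave for unrelated reasons and are replaced, subjects with data give 2/8 = 25% against a true 2/10 = 20%. The error then runs the other way.

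**The case against.** The strongest case against is that stoppers remain visible elsewhere, and that case largely stands. The Safety Analysis Set keeps every dosed subject, replaced or not (SAP 5.2), and all safety outputs use it (SAP 16). Disposition gives reasons for early discontinuation by cohort (SAP 9). Adverse events leading to discontinuation are summarised and listed (SAP 16.1.2 and 16.1.3). The dosing diary also records subject-reported events (protocol 5.7.1). A reader might infer that aquaresis-related withdrawals vanish from the report; they do not. What these outputs lack is the symptom-burden answer itself, which is what the questionnaire adds to the endpoint.

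Other stronger readings are tempting but unsupported:
- *Early stoppers give no multiple-dose answer.* The Day 2 form already follows both Day 1 doses. Only the later answer is lost.
- *The bias always favours the drug.* Protocol 4.2.1 lists many other reasons for leaving, including noncompliance, loss to follow-up and withdrawn consent. Only stops caused by aquaresis have a predictable direction.
- *The plan will report 25% whatever happens.* SAP 6.1 leaves the denominator open, so 25% is one of two permitted results.
- *The dose comparison is distorted.* A larger effect at 200 mg BID is a reasonable inference, but no figure in the documents supports it, and SAP 16 plans no statistical comparison between groups for safety data.
- *Replacements are picked because they tolerate the drug.* Replacement is discretionary, and nothing says so.

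Protocol 6.1 lets the investigator add safety assessments, but that does not require the form. The questionnaire and any instructions for early stoppers sit in a study reference manual that is not among the documents, so its recall period is unknown.

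**Conclusion.** The gap in the schedule is certain: it follows from the two tables and both ET definitions. Its consequence is limited to the post-Day 2 questionnaire result, one component of a primary endpoint in a descriptive study. For stops caused by aquaresis, the Day 7 proportions understate burden under both denominators that SAP 6.1 allows. With the assumed 2 high-burden answers in 8 and one to three replaced stoppers, the result is 25%, or 22% to 18%, against 33% to 45%. These figures assume that every stopper would have reported high burden; the number of stoppers is also assumed. For stops with other causes the direction is unknown. The change should be made because it is cheap and because the SAP's own estimand calls for the data. The documents do not support a claim that the safety report as a whole is biased.

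**What to change.** **Protocol.** Reconcile 4.2.1 and 4.2.2 into a single ET assessment list and include the existing questionnaire in it. A subject who stops before the Day 7 form completes it as soon as possible after the last dose, with reference to the time on drug. Carry this into Tables 12-1 and 12-2.

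**Non-PK/PD SAP 16.7.**
- Report Day 7 answers and ET answers separately, and also combined as *Day 7 or ET (last available)*.
- State the denominator: all dosed subjects, including those later replaced.
- Show beside these the number who stopped before Day 7 for aquaresis-related reasons.
- Confirm that Day 2 answers are presented. The visit list in SAP Appendix 1, as it reads here, has no Day 2 entry.

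**Cost.** One short existing form at a visit already requested, and a few sentences in the SAP. ET forms will be completed on varying study days and after drug has stopped, so the combined summary should be read alongside the separate ones. The recall wording should be checked against the study reference manual before the two are pooled.

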This section lists corrections of typos, text changes for consistency or other clarifications. These changes do not affect clinical decision making or consent.

Page	Section	Version 3 dated April 24, 2018	Version 4	Explanation
26	4.1.2 – Exclusion criteria	1. Subjects with known sensitivity or idiosyncratic reaction to any compound present in lixivaptan, its related compounds such as benzazepines (e.g., tolvaptan, conivaptan, benazepril, fenoldopam, mesylate , or mirtazapine), or any compound listed as being present in the study formulation.	1. Subjects with known sensitivity or idiosyncratic reaction to any compound present in lixivaptan, its related compounds such as benzazepines (e.g., tolvaptan, conivaptan, benazepril, fenoldopam, or mirtazapine), or any compound listed as being present in the study formulation.	Deletion of mesylate , the counter-ion of fenoldopam
27	4.1.2 – Exclusion criteria	18. Subjects have experienced an illness that is considered by the Investigator to be clinically significant within 2 weeks of study drug administration on Day 1.	19. Subjects who have experienced an illness that is considered by the Investigator to be clinically significant within 2 weeks of study drug administration on Day 1.	
39	6.1.6 – MRI Assessment	Given the importance of performing the second MRI assessment within a short time interval after the last dose of study medication (PM dose on Day 7), all MRI assessments will be scheduled for each subject in conjunction with the Screening visit.	Given the importance of performing the second MRI assessment within a short time interval after the last dose of study medication (PM dose on Day 7), it is recommended that all MRI assessments be scheduled for each subject at the time of the Screening visit.	
61	12 - APPENDICES	This study uses the 2009 CKD-EPI creatinine equation, ¹⁶ which is recommended by the KDIGO Clinical Practice Guidelines for Management of Chronic Kidney Disease ³ .	This study uses the 2009 CKD-EPI creatinine equation, ¹⁶ which is recommended by the KDIGO Clinical Practice Guidelines for Management of Chronic Kidney Disease.	Deletion of reference at end of sentence.

Clinically-relevant Changes

This section describes changes that affect the type or frequency of protocol procedures, or the addition of information to the protocol that influences clinical decision making or consent.

Page	Section	Version 3 dated April 24, 2018	Version 4	Comments
9	Synopsis	The subjects will be male or female, between 18 and 60 years of age.	The subjects will be male or female, between 18 and 65 years of age.	Increases the eligible age for inclusion into the study to 65 years.
22	3.1 - Study Design	Subjects will be allowed to re-screen for the study for up to two times.	Subjects may be allowed to re-screen or have repeat testing after agreement between the investigator and medical monitor.	Introduces more flexibility in screening procedures.
24	4.1.1 – Inclusion Criteria	2. Male or female, between 18 and 60 years of age (inclusive) at the time of Screening.	2. Male or female, between 18 and 65 years of age (inclusive) at the time of Screening.	Increases the eligible age for inclusion into the study to 65 years.
25	4.1.1 – Inclusion Criteria	Double barrier methods of non-hormonal contraception are permitted in this study. Acceptable forms of contraception include the following: 
 intrauterine device 	Double barrier methods of non-hormonal contraception are permitted in this study. Acceptable forms of contraception include the following: 
 intrauterine device, including Mirena® 	Clarifies that use of the low progesterone-releasing intrauterine device Mirena is allowed.
25	4.1.1 – Inclusion Criteria	Hormonal contraception is not permitted in this pharmacokinetic study due to the potential for	Estrogen-based hormonal contraception is not permitted in this pharmacokinetic study due to	Limits hormonal contraception exclusion to estrogen-containing contraceptives. Progesterone-only

Page	Section	Version 3 dated April 24, 2018	Version 4	Comments
		interaction with lixivaptan.	the potential for interaction with lixivaptan.	contraceptives are allowed.
27	4.1.2. – Exclusion criteria	15. Subjects with aspartate aminotransferase (AST), alanine aminotransferase (ALT), gamma-glutamyltransferase (GGT), alkaline phosphatase (ALP) or total bilirubin $\geq 1.0 \times$ upper limit of normal (ULN) at Screening.	15. Subjects with aspartate aminotransferase (AST), alanine aminotransferase (ALT), gamma-glutamyltransferase (GGT), alkaline phosphatase (ALP) or total bilirubin $\geq 1.0 \times$ upper limit of normal (ULN) at Screening. Subjects with elevated bilirubin due to Gilbert's Syndrome may be allowed at the discretion of the Investigator.	Allows inclusion of subjects with elevated bilirubin due to Gilbert's Syndrome at the discretion of the Investigator.
27	4.1.2. – Exclusion criteria	17. Subjects with contraindications to or interference with MRI assessments (ferromagnetic metal prostheses, aneurysm clips, severe claustrophobia, or large abdominal/back tattoos. Investigator should seek MRI safety guidance from local MRI facility).	18. Subjects with contraindications to or interference with MRI assessments (ferromagnetic metal prostheses, aneurysm clips, severe claustrophobia, or large abdominal/back tattoos) will be excused from this procedure, but may participate in the study providing that all other eligibility criteria are met. Investigator should seek MRI safety guidance from local MRI facility.	Allows inclusion of subjects with contraindications to or interference with MRI assessments provided they meet all other inclusion criteria. Clarifies that no MRI tests will be conducted on these subjects.
28	4.1.2. – Exclusion criteria		26. Subjects who have experienced elevated AST or ALT (defined as $\geq 2.0 \times$ ULN) while taking tolvaptan.	Adds exclusion of subjects who have shown signs of liver toxicity on tolvaptan therapy.

Page	Section	Version 3 dated April 24, 2018	Version 4	Comments
32	5.4 – Identity of Investigational Product	Batch 17120A	Batch 17121A1	Clarifies batch number of investigational product.
37	5.9 - Diet, Fluid, and Activity Control	Due to the expected aquaretic effects of lixivaptan, subjects should be reminded to maintain adequate fluid intake and be mindful of their thirst status at each study visit. Subjects should be instructed to replenish fluids with each void and aim to drink 4-5 liters of fluid per day, or as needed to maintain adequate hydration.	During Days -2 and -1 of CRU confinement, subjects should continue consuming their usual amount of fluids. Due to the expected aquaretic effects of lixivaptan, subjects should be reminded to maintain adequate fluid intake and be mindful of their thirst status at each study visit starting with Day 1 of CRU confinement. Subjects should be instructed to replenish fluids with each void and aim to drink 4-5 liters of fluid per day, or as needed to maintain adequate hydration, while taking lixivaptan.	Clarifies fluid intake recommendations before the first dose of study drug and while taking study drug.
39	6.1.4 - 12-Lead Electrocardiograms	Electrocardiograms will be obtained with the subject remaining in a semi-recumbent position following 5 minutes of rest.	Electrocardiograms will be obtained with the subject remaining in a supine or semi-recumbent position following 5 minutes of rest. All electrocardiograms throughout the study for a given subject should be measured in the same position, i.e. either all in a supine position or all in a semi-recumbent position.	Allows supine position for electrocardiograms provided that the same position is maintained for the same subject throughout the study.

Page	Section	Version 3 dated April 24, 2018	Version 4	Comments
40	6.1.6 – MRI Assessment		Occasionally, patients may be unable to continue into the study after completing their Screening visit and baseline MRI assessment (for example, due to personal circumstances or for not meeting laboratory inclusion criteria). These patients may subsequently qualify for the study and be rescreened at a later time. In this case, their prior baseline MRI assessment may be used instead of obtaining a new baseline MRI scan; provided, however, that no more than 8 weeks have elapsed from the time of the initial MRI assessment until admission into the CRU.	Clarifies that the baseline MRI assessment completed by patients who subsequently screen fail or are otherwise unable to continue into the study is valid for a period of 8 weeks. Patients who successfully rescreen must be admitted into the CRU within 8 weeks from the original MRI assessment date for such MRI to be considered valid.
41	6.1.6 – MRI Assessment	Subjects with ferro-magnetic prostheses, aneurysm clips, severe claustrophobia or other contraindications or exclusions interfering with MRI measurements will be excluded from study participation.	Subjects with ferro-magnetic prostheses, aneurysm clips, severe claustrophobia or other contraindications or exclusions interfering with MRI measurements will be excused from this procedure, but may participate in the study providing that all other eligibility criteria are met. Investigator should seek MRI safety guidance from the local MRI facility.	Allows inclusion of subjects with contraindications to or interference with MRI assessments provided they meet all other inclusion criteria. Clarifies that no MRI tests will be conducted on these subjects.

Page	Section	Version 3 dated April 24, 2018	Version 4	Comments
62	Footnote 2 to Table 12-1 - Schedule of Assessments	2. Serum pregnancy test to be performed at Screening; Urine pregnancy test to be performed at Day -2 or Day -1.	2. Serum pregnancy test to be performed at Screening; Urine pregnancy test to be performed at Day -2 or Day -1 and at End of Study.	Clarifies nature of pregnancy test at End of Study visit.
63	Footnote 7 to Table 12-1 – Schedule of Assessments	Electrocardiograms to be obtained following 5 minutes rest in semi-recumbent position.	Electrocardiograms to be obtained following 5 minutes rest in supine or semi-recumbent position. The same position must be used throughout the study for a given subject.	Allows supine position for electrocardiograms provided that the same position is maintained for the same subject throughout the study.
63	Table 12-2 - Assessment Windows. PK Blood Samples – Assessment Day	Day 1, Day 2, Day 4, Day 6, Day 7, Day 8, Day 9	Day 1, Day 2, Day 4, Day 6, Day 7, Day 8, Day 9, Day 11	Adds Day 11 to the Assessment Window table.
65	Table 12-2 - Assessment Windows. PK Blood Samples – Window (units)	- 60 minutes (predose Day 1) - 10 minutes (predose Day 7) ± 3 min (< 1-4 hr) ± 5 min (> 4-12 hr) ± 10 min (> 12-24 hr) ± 1 hr (> 24-48 hr) ± 2 hr (> 48-96 hr)	- 60 minutes (predose Day 1) - 10 minutes (predose Day 7) ± 3 min (≤ 4 hr) ± 5 min (> 4 hr but ≤ 12 hr) ± 10 min (> 12 hr but ≤ 24 hr) ± 1 hr (> 24 hr but ≤ 48 hr) ± 2 hr (> 48)	Clarifies the appropriate time window for time values that lie on the extremes of each time interval.
